**Table 2 Study Drug Dosing Information**

Cohort	Treatment	Volume to Administer/Dose	# Doses	Total ISIS 681257
A	20 mg ISIS 681257 or placebo (Every 4 weeks)	0.2 mL	≤ 13	≤ 260 mg
B	40 mg ISIS 681257 or placebo (Every 4 weeks)	0.4 mL	≤ 13	≤ 520 mg
C	60 mg ISIS 681257 or placebo (Every 4 weeks)	0.6 mL	≤ 13	≤ 780 mg
D	20 mg ISIS 681257 or placebo (Every 2 weeks)	0.2 mL	≤ 26	≤ 520 mg
E	20 mg ISIS 681257 or placebo (Every week)	0.2 mL	≤ 52	≤ 1040 mg

## 8.2 Other Protocol-Required Drugs

No other Study Drug treatments are required by the protocol.

## 8.3 Other Protocol-Required Treatment Procedures

No other treatment procedures are required by the protocol.

## 8.4 Treatment Precautions

No specific treatment precautions are required.

## 8.5 Safety Monitoring Rules

Please refer also to the “Guidance for Investigator” section of the Investigator’s Brochure.

For the purposes of safety monitoring baseline is defined as the average of the pre-dose test closest to Day 1 and the Day 1 value itself.

In addition to the standard monitoring of clinical safety parameters, the following guidelines are provided for the monitoring of selected parameters chosen based on preclinical and clinical observations.

In case of discrepancy between the test results from 2 sources, such as between the central and local lab, safety-mandated action must be initiated based on the more critical (lower or higher, as relevant) of the 2 values.

**Confirmation Guidance:** At any time during the study (treatment or post-treatment follow-up periods), the clinical laboratory results meeting any of the safety monitoring criteria presented below **must be confirmed** by performing measurements (ideally in the same laboratory that performed the initial measurement) on new specimens prior to administering the next dose of Study Drug (ISIS 681257 or placebo). All new specimen collections should take place as soon as possible (ideally within 3 days of the initial collection).

In addition, as described in [Section 6.2.1](#) hematology labs should be sent in parallel to the central and local laboratory for analysis.

**Stopping Rule Guidance:** The Investigator may interrupt or permanently discontinue study treatment for any medical reason including changes in clinical laboratory results.

In the event of an initial clinical laboratory result that meets a stopping criterion, patients must not be re-dosed until a confirmatory test result has been reviewed by the Study Medical Monitor. If any of the stopping criteria described below (refer to [Sections 8.6.1](#) to [8.6.3](#)) are met and are confirmed, the patient will be permanently discontinued from further treatment with Study Drug (ISIS 681257 or placebo), evaluated fully as outlined below and in consultation with the Study Medical Monitor or appropriately qualified designee, and will be entered into the post-treatment evaluation portion of the study. In general, patients who do not meet the stopping rules based upon retest may continue dosing. However, the Investigator and the Study Medical Monitor (or appropriately qualified designee) should confer as to whether additional close monitoring of the patient is appropriate.

**Additional Guidance:** If possible, a PK sample should be collected as soon as possible after an SAE has occurred (preferably within 2 weeks). In addition, if a patient is asked to return to the clinic for additional evaluations due to an AE, then a PK sample should be taken at the time of the unscheduled visit.

### **8.5.1 Safety Monitoring Rules for Liver Chemistry Tests**

The following rules are adapted from the FDA guidance for industry, “Drug-Induced Liver Injury: Premarketing Clinical Evaluation,” issued by the U.S. Department of Health and Human Services, Food and Drug Administration, July 2009. For a definition of Baseline, please refer to guidance in [Section 8.5](#) above.

All patients will have liver chemistry tests monitored every 2 weeks for the first 3 months of the study treatment, and monthly thereafter during the Treatment Period.

In the event of appearance of symptoms or signs of hepatic injury (jaundice, fatigue, nausea, vomiting, right upper quadrant pain or tenderness, fever, rash, abnormal bleeding or bruising, or eosinophilia > ULN) liver enzymes and bilirubin should be tested as soon as possible. Testing at a lab that is local to the patient is permissible for this purpose.

In the event of an ALT or AST measurement that is  $> 3 \times$  ULN (or the greater of  $2 \times$  baseline value or  $3 \times$  ULN if the baseline value was  $>$  ULN) at any time during the study (treatment or post-treatment period), the initial measurement(s) should be confirmed as described in Section 8.5.

Patients with confirmed ALT or AST levels  $> 3 \times$  ULN should have their liver chemistry tests (ALT, AST, ALP, international normalized ratio [INR] and total bilirubin) retested at least once-weekly until ALT and AST levels become  $\leq 1.2 \times$  ULN.

All results of liver function tests must be reviewed promptly (within 24 hours of receipt) by the Investigator or the designee to ensure that the result has not met the stopping rules per Section 8.6.1.

Further Investigation into Liver Chemistry Elevations: For patients with confirmed ALT or AST levels  $> 3 \times$  ULN, the following evaluations should be performed:

1. Obtain a more detailed history of symptoms and prior and concurrent diseases
2. Obtain further history for concomitant drug use (including nonprescription medications, herbal and dietary supplement preparations), alcohol use, recreational drug use, and special diets
3. Obtain a history for exposure to environmental chemical agents and travel
4. Serology for viral hepatitis (hepatitis A virus [HAV] immunoglobulin M [IgM], hepatitis B surface antigen [HBsAg], hepatitis C virus [HCV] antibody, Cytomegalovirus [CMV] IgM, and EBV antibody panel)
5. Serology for autoimmune hepatitis (e.g., antinuclear antibody [ANA])

Additional liver evaluations, including gastroenterology/hepatology consultations, hepatic CT or MRI scans, may be performed at the discretion of the Investigator, in consultation with the Sponsor Medical Monitor and the study DSMB. Repetition of the above evaluations should be considered if a patient's ALT and/or AST levels reach  $5 \times$  ULN.

All routine liver function test results will be reviewed on an ongoing basis at the weekly safety review by the Medical Monitor.

All lab alerts for abnormal liver function tests must be promptly (within 24 hours of receipt) reviewed by the Investigator and Medical Monitors.

Lab alerts for abnormal liver chemistry tests will be issued for: 1) ALT or AST  $> 3 \times$  ULN; 2) ALT or AST  $> 2 \times$  baseline; 3) total bilirubin  $> 3 \times$  ULN; 4) ALP  $> 3 \times$  ULN. These alert levels are set to anticipate the risk of a combined elevation of aminotransferases and bilirubin as per the FDA Guidance referenced in Section 8.5.1.

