### **8.6.1 Stopping Rules for Liver Chemistry Elevations**

In the event of confirmed laboratory results meeting any of the following criteria, dosing of a patient with Study Drug will be stopped permanently:

1. ALT or AST > 8 x ULN, which is confirmed
2. ALT or AST > 5 x ULN, which is confirmed and persists for  $\geq 2$  weeks
3. ALT or AST > 3 x ULN (or the greater of 2 x Baseline value or 3 x ULN if the Baseline value was > ULN), which is confirmed **and** total bilirubin > 2 x ULN or INR > 1.5
4. ALT or AST > 3 x ULN (or the greater of 2 x Baseline value or 3 x ULN if the Baseline value was > ULN), which is confirmed, and the new appearance (i.e., onset coincides with the changes in hepatic enzymes) of fatigue, nausea, vomiting, right upper quadrant pain or tenderness, fever, rash, or eosinophilia (> ULN) felt by the Investigator to be potentially related to hepatic inflammation

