Alanine aminotransferase increased	>ULN - 3.0 x ULN	>3.0 - 5.0 x ULN	>5.0 x ULN
Alkaline phosphatase increased	>ULN - 2.5 x ULN	>2.5 - 5.0 x ULN	>5.0 x ULN
Alkalosis	pH >normal, but ≤7.5	-	pH >7.5
Aspartate aminotransferase increased	>ULN - 3.0 x ULN	>3.0 - 5.0 x ULN	>5.0 x ULN
Blood bilirubin increased	>ULN - 1.5 x ULN	>1.5 - 3.0 x ULN	>3.0 x ULN
Cardiac troponin I increased	Levels above the upper limit of normal and below the level of myocardial infarction as defined by the manufacturer	-	Levels consistent with myocardial infarction as defined by the manufacturer

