Additional liver evaluations, including gastroenterology/hepatology consultations, hepatic CT or MRI scans, may be performed at the discretion of the Investigator, in consultation with the Sponsor Medical Monitor and the study DSMB. Repetition of the above evaluations should be considered if a patient's ALT and/or AST levels reach 5 x ULN.

All routine liver function test results will be reviewed on an ongoing basis at the weekly safety review by the Medical Monitor.

All lab alerts for abnormal liver function tests must be promptly (within 24 hours of receipt) reviewed by the Investigator and Medical Monitors.

Lab alerts for abnormal liver chemistry tests will be issued for: 1) ALT or AST > 3 x ULN; 2) ALT or AST > 2 x baseline; 3) total bilirubin > ULN; 4) ALP > ULN. These alert levels are set to anticipate the risk of a combined elevation of aminotransferases and bilirubin as per the FDA Guidance referenced in [Section 8.5.1](#).

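### The total bilirubin lab alert (> 3 x ULN) lies above the bilirubin level in the combined liver stopping rule (> 2 x ULN), so it cannot give the early warning the protocol states for it

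*Protocol*

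**What the plan says.** Section 8.5.1 of the current protocol (Amendment 6) issues a liver lab alert in four situations: ALT or AST above 3 x ULN; ALT or AST above twice baseline; "total bilirubin $> 3 \times$ ULN"; and ALP above 3 x ULN. It gives the purpose directly afterwards: "These alert levels are set to anticipate the risk of a combined elevation of aminotransferases and bilirubin", with a reference to the FDA guidance from which the section's rules are adapted.

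In Section 8.6.1, criterion 3 is met when ALT or AST is confirmed above 3 x ULN (or above the greater of 2 x baseline and 3 x ULN if baseline was above ULN) and there is also "total bilirubin > 2 x ULN or INR > 1.5". The consequence is that "dosing of a patient with Study Drug will be stopped permanently".

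Two other provisions bear on the point. Section 8.5.1 also says "All results of liver function tests must be reviewed promptly (within 24 hours of receipt) by the Investigator or the designee", and it adds a weekly Medical Monitor review of routine liver results. Section 6.2.1 sends lab alerts at the same time to the investigator, the sponsor and CRO medical monitors and the sponsor's drug safety physician. For an actionable alert, the CRO monitor's instructions follow within 24 hours.

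**The concern.** An alert that is meant to anticipate an event should fire before the event's components are reached. Here the bilirubin alert starts at a higher level than the bilirubin component of the one combined rule in the protocol, so for bilirubin the order of warning and action is reversed.

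The other alert families run the other way. The renal alert is issued at a fall in estimated creatinine clearance of more than 25%, against more than 40% in the renal stopping rule (Sections 8.5.2 and 8.6.2). The platelet alert is issued below 140,000/mm³, while the first dose change in Table 3 comes below 100,000/mm³.

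What is at stake is time. An alert prompts immediate notice to the medical monitors and instructions within a day. Without one, a patient whose bilirubin and aminotransferases are both rising depends on the investigator's own reading and the weekly review. After the first three months, scheduled liver tests are monthly.

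**Working it through.** No sample size, power or event count is involved. The check sets the thresholds side by side.

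**Inputs**

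| Quantity | Alert (8.5.1) | Criterion 3 (8.6.1) |
|---|---|---|
| ALT or AST | > 3 x ULN, or > 2 x baseline | confirmed > 3 x ULN; if baseline > ULN, the greater of 2 x baseline and 3 x ULN |
| Total bilirubin | > 3 x ULN | > 2 x ULN (or the INR limb) |

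**Step 1: order of the bilirubin levels.** Alert level divided by stopping component is 3 / 2 = 1.5. Any value that fires the bilirubin alert already exceeds 2 x ULN. Between 2 x ULN (exclusive) and 3 x ULN (inclusive), the bilirubin part of criterion 3 is satisfied and no bilirubin alert is issued.

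**Step 2: can criterion 3 be met with no listed alert?** No. Its aminotransferase part is never below 3 x ULN, whatever the baseline, and a value above 3 x ULN is itself the first listed alert.

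**Step 3: where is early warning lost?** No aminotransferase alert fires while ALT and AST are each at or below the smaller of 3 x ULN and 2 x their baseline B. Section 5.2 admits patients with ALT and AST up to 2.0 x ULN, so:

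- B = 0.5 x ULN: no alert up to min(3, 1.0) = 1.0 x ULN
- B = 1.0 x ULN: no alert up to min(3, 2.0) = 2.0 x ULN
- B = 1.5 x ULN: no alert up to min(3, 3.0) = 3.0 x ULN
- B = 2.0 x ULN: no alert up to min(3, 4.0) = 3.0 x ULN

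Each of these leaves room for a rise without an alert. With B above 0.5 x ULN, the unalerted range includes values above normal.

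**Step 4: an illustration (assumed values).** Take baseline ALT 1.5 x ULN, ALT now 2.5 x ULN, bilirubin 2.5 x ULN, AST below its alert levels and ALP at or below 3 x ULN.

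- ALT > 3 x ULN? 2.5 is not above 3.
- ALT > 2 x baseline? 2 x 1.5 = 3.0, and 2.5 is not above 3.0.
- Bilirubin > 3 x ULN? 2.5 is not above 3.
- ALP > 3 x ULN? No, by assumption.

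None of the four alerts fires, although both components are raised and bilirubin is already above its level in criterion 3. Criterion 3 itself is not met, because ALT is not above 3 x ULN. This is a developing combined elevation, the situation the alerts are said to anticipate.

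**The case against.** The strongest reply is that the alerts work as a set. Criterion 3 cannot be reached without an aminotransferase value that fires an alert, and the alert at twice baseline can fire well before 3 x ULN. Once ALT or AST above 3 x ULN is confirmed, bilirubin and INR are retested at least weekly. An isolated bilirubin between 2 and 3 x ULN meets no stopping rule. The investigator's 24-hour check and the weekly Medical Monitor review apply whether or not an alert is issued. Section 6.2.1 also mentions alerts issued under stopping rules, so the list in Section 8.5.1 may not be the only liver trigger. All of this stands, and it limits the consequence.

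It can also be said that Section 8.5.1 ties the alerts to the FDA guidance and does not name Section 8.6.1. That is correct, so the link to criterion 3 is an inference. It is a sound one, because the protocol has no other rule combining aminotransferases and bilirubin.

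A reader might infer more than the documents support:

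- *That a patient could meet the stopping rule unnoticed.* Step 2 of the working excludes this for the listed alerts.
- *That the counts of patients meeting liver stopping rules, and hence dose selection, are distorted* (Sections 10.1.3 and 10.1.4). Nothing derives those counts from alerts, and an alert level does not change the recorded laboratory values.
- *That the alert conflicts with Appendix D, where bilirubin above 3.0 x ULN is graded severe.* Appendix D grades adverse events and does not set alert levels.
- *That the lower bilirubin alert level in the superseded Amendment 5 text shows which level is right.* A difference from superseded text is not an error and settles nothing.

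**Conclusion.** The inconsistency is real and lies within the current text. The bilirubin alert cannot by itself do what Section 8.5.1 says the alert levels are for, because it starts at 1.5 times the bilirubin component of the combined stopping rule. What is lost is early warning for patients with bilirubin above 2 and up to 3 x ULN whose aminotransferases are rising but not yet at an alert level. Detection of the stopping rule itself is not lost.

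The conclusion rests on reading criterion 3 as the combined elevation the alerts are meant to anticipate, and on the four alerts in Section 8.5.1 being the ones that operate before a stopping rule is met. The protocol gives no bilirubin distribution, so the number of patients affected cannot be estimated. The point is modest in size but concerns patient safety and is cheap to correct.

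**What to change.** Reconcile the liver alert list in Section 8.5.1, and the sentence stating its purpose, with stopping criterion 3 in Section 8.6.1. Which level or which wording changes, and in what direction, is for the sponsor's clinicians to decide. This review proposes no threshold. Then align the central laboratory's alert specification with the result and record the change in the summary of changes.

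The cost is an edit to the protocol text, a change to the laboratory alert configuration if levels move, and possibly some additional alerts for the investigators and medical monitors to review.

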### **8.5.2 Safety Monitoring for Renal Function**

While on treatment all patients will have renal function tests monitored every 2 weeks throughout the study. Upon completion of the study treatment period, urine renal biomarkers should be monitored every 2 weeks for the first 6 weeks and then at 10 and 16 weeks post treatment period (as per visit schedule).

In the event of appearance of symptoms or signs consistent with renal dysfunction such as hematuria, polyuria, anuria, flank pain, new-onset hypertension, nausea and/or anorexia, renal function should be tested as soon as possible. Testing at a lab that is local to the patient is permissible for this purpose.

While on treatment during the course of the study, urinary surveillance will include urinalysis to include urine albumin/creatinine ratio (UACR), urine protein/creatinine ratio (UPCR) and urinary red blood cells (RBCs), as well as serum creatinine and cystatin-C to estimate glomerular filtration rate (eGFR), which will be monitored every 2 weeks. In addition, biomarkers of acute renal injury will also be measured every 2 weeks ([Appendix B](#)).

The assessment of serum creatinine, cystatin-C, and urinalysis more frequently than every 2 weeks will be guided by consultation with a local nephrologist. Any decision taken by the Investigator to discontinue study medication will be made taking into account all available and relevant data. In addition, the decision to discontinue Study Drug may also be based on lesser changes in these parameters observed in isolation or in association with other renal-related abnormalities. Any decision taken to restart study medication will be made in consultation with the Study Medical Monitor taking into account all available and relevant data.

All renal function test results will be reviewed on an ongoing basis at the weekly safety review by the Medical Monitor.

All results of renal function tests must be reviewed promptly (within 24 hours of receipt) by the Investigator or the designee to ensure that the result has not met the stopping rules per [Section 8.6.2](#).

Lab alerts for abnormal renal tests will be issued for: Creatinine clearance (by CKD-EPI formula) decrease from baseline > 25%, urine albumin/creatinine ratio (UACR) > 250 mg/g, urine protein/creatinine ratio (UPCR) > 0.5 mg/mg, or an increase in serum creatinine from baseline > 0.3 mg/dL).

These alert levels are set to anticipate and prevent the risk of a medically significant change in renal function while receiving Study Drug.

In the event of a confirmed (as described in [Section 8.5](#)) laboratory result meeting one or more of the above criteria, dosing with the Study Drug should be interrupted and the Study Medical Monitor informed. In addition, the following supplemental renal tests should be immediately obtained:

Serum creatinine, urine culture, 24-hour urine sample for creatinine clearance, urine albumin and urine protein, urine microscopy sample with inspection of sediment.

The Investigator should also review the patient's concomitant medications for potentially nephrotoxic agents, and, with the results of these evaluations, review any decision to continue or discontinue the patient in consultation with the Study Medical Monitor and the medical area specialist consultant of the DSMB.

#### **8.5.4 Safety Monitoring for Minor Bleeding Events**

Patients will be instructed to promptly report any signs or symptoms of bleeding. Minor bleeding events are those that do not fulfill the criteria for major bleeding or clinically-relevant, non-major bleeding events (which are defined in [Section 8.6.3](#)), for example excess bruising, petechiae, or gingival bleeding on brushing teeth. If a minor bleeding event occurs, the Investigator must notify the Sponsor Medical Monitor and additional testing of coagulation parameters activated partial thromboplastin time (aPTT), prothrombin time (PT), INR, hepatic enzymes, bilirubin and platelet count should be performed.

#### **8.5.5 Safety Monitoring for Constitutional Symptoms**

Patients will be instructed to promptly report any signs or symptoms of fever, constitutional symptoms, rash, arthralgia or joint swelling that may arise during the study and the Investigator should closely evaluate all potential causes, including concomitant illness. Patients who experience persistent symptoms should be discussed with the Sponsor Medical Monitor or designee to determine whether additional monitoring or laboratory tests are required.

### **8.6 Stopping Rules**

For the purposes of stopping rules, Baseline is defined as the average of Day 1 pre-dose assessment and the last measurement prior to Day 1.

### **8.6.1 Stopping Rules for Liver Chemistry Elevations**

In the event of confirmed laboratory results meeting any of the following criteria, dosing of a patient with Study Drug will be stopped permanently:

1. ALT or AST > 8 x ULN, which is confirmed
2. ALT or AST > 5 x ULN, which is confirmed and persists for  $\geq 2$  weeks
3. ALT or AST > 3 x ULN (or the greater of 2 x Baseline value or 3 x ULN if the Baseline value was > ULN), which is confirmed **and** total bilirubin > 2 x ULN or INR > 1.5
4. ALT or AST > 3 x ULN (or the greater of 2 x Baseline value or 3 x ULN if the Baseline value was > ULN), which is confirmed, and the new appearance (i.e., onset coincides with the changes in hepatic enzymes) of fatigue, nausea, vomiting, right upper quadrant pain or tenderness, fever, rash, or eosinophilia (> ULN) felt by the Investigator to be potentially related to hepatic inflammation

### **8.6.2 Stopping Rules for Renal Function Test Results**

In the event of an estimated creatinine clearance (by CKD-EPI formula) meeting any of the following criteria, or any change in renal biomarkers deemed by the nephrologist on the DSMB to require further evaluation, a serum creatinine, urine culture, 24-hour urine sample for creatinine clearance and protein, and urine microscopy sample with inspection of sediment should be immediately obtained:

1. CKD-EPI decrease of > 40% from Baseline
2. CKD-EPI value < 45 mL/min/1.73 m^2

Dosing of a patient with Study Drug (ISIS 681257 or placebo) will be stopped permanently if 24-hour urine testing confirms any of the following values in the absence of an alternative explanation:

1. Urine protein is > 1.0 g
2. Creatinine clearance decrease of > 40% from baseline
3. Creatinine clearance < 45 mL/min/1.73 m^2

Irrespective of whether the stopping rule is confirmed or not, the follow-up schedule and frequency of renal function monitoring after the initial event will be determined by the Study Medical Monitor in consultation with the Investigator and the medical area specialist on the DSMB. The Investigator should consider consulting a local nephrologist for any change of renal function that presents a concern. If a renal biopsy is performed, a sample specimen should be made available for examination by an independent renal pathologist who has been engaged by the Sponsor to review such specimens.

